 - Hematologic intolerance: Patients with grade 3 or 4 toxicity (absolute neutrophil count [ANC] or platelets) while on therapy that is recurrent after dose reduction to the lowest doses recommended by manufacturer
6. Eastern Cooperative Oncology Group (ECOG) performance status (PS) of 0, 1, or 2
7. Adequate end organ function as defined by (as per central laboratory tests):
 - Total bilirubin $\leq 1.5 \times$ ULN except for patients with Gilbert's syndrome who may only be included if total bilirubin $\leq 3.0 \times$ ULN or direct bilirubin $\leq 1.5 \times$ ULN

- Aspartate transaminase (AST) $\leq 3.0 \times \text{ULN}$
 - Alanine transaminase (ALT) $\leq 3.0 \times \text{ULN}$
 - Serum lipase $\leq 1.5 \times \text{ULN}$. For serum lipase $> \text{ULN} - \leq 1.5 \times \text{ULN}$, value must be considered not clinically significant and not associated with risk factors for acute pancreatitis
 - Alkaline phosphatase $\leq 2.5 \times \text{ULN}$
 - Creatinine clearance $\geq 50 \text{ mL/min}$ as calculated using Cockcroft-Gault formula
8. Patients must avoid consumption of grapefruit, Seville oranges or products containing the juice of each during the entire study and preferably 7 days before the first dose of study medications, due to potential CYP3A4 interaction with the study medications. Orange juice is allowed.
9. Written informed consent obtained prior to any screening procedures.
- 10a. Patients must have the following electrolyte values (as per central laboratory tests) within normal limits or corrected to be within normal limits with supplements prior to first dose of study medication:
- Potassium (potassium increase of up to 6.0 mmol/L is acceptable at study entry if associated with creatinine clearance within normal limits)
 - Total calcium (corrected for serum albumin); (calcium increase of up to 12.5 mg/dl or 3.1 mmol/L is acceptable at study entry if associated with creatinine clearance within normal limits)
 - Magnesium, with the exception of magnesium increase $> \text{ULN} - 3.0 \text{ mg/dL}$; $> \text{ULN} - 1.23 \text{ mmol/L}$ associated with creatinine clearance (calculated using Cockcroft-Gault formula) within normal limits.
11. Evidence of typical BCR-ABL1 transcript [e14a2 and/or e13a2] at the time of screening which are amenable to standardized RQ-PCR quantification.

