6.3 Dose modifications

6.3.1 Dose modification and dose delay

For patients who do not tolerate the protocol-specified dosing schedule, dose interruptions and/or reductions are either recommended or mandated in order to allow the patient to continue the study treatment.

These dose modifications are summarized in [Table 6-2](#). The dose reduction indicated as “recommendations” are provided to assist investigators in the event the patient experiences toxicity. However, deviations from “mandatory” dose interruptions and/or reductions are not allowed and mandatory interruptions or reductions must be strictly followed. Re-escalation to asciminib 40 mg BID is permitted if a change in the patient’s individual benefit/risk assessment at the lower dose level is seen. Re-escalation will be allowed only once for any given patient on the asciminib arm per protocol. Permanent treatment discontinuation is mandatory for specific events indicated as such in [Table 6-2](#). Any dose changes must be recorded on the Dosage Administration Record eCRF.

A patient must discontinue treatment with either asciminib or bosutinib if, after treatment is resumed at a lower dose level, the toxicity recurs with the same or worse severity, except for recurrence of cytopenias ([Table 6-2](#)). If a patient requires a dose interruption of > 28 days for each non-hematologic toxicity, then the patient must be discontinued from the study treatment. If a hematologic toxicity (cytopenia Grade 3 or 4) lasts for more than 42 days without recovery to at least a Grade 2, despite TKI interruption and adequate management (including hematopoietic growth factors), then the patient must be discontinued from the study treatment.

Table 6-2 Criteria for dose reduction/interruption and re-initiation of asciminib and bosutinib treatment for adverse drug reactions

[figure not shown]
Dose modifications for both asciminib and bosutinib		
Please note that if a patient requires a dose interruption of > 28 days for each toxicity, then the patient must be discontinued from the study treatment		
Worst toxicity CTCAE Grade 4.03	Asciminib	Bosutinib
Investigations (Hematologic) If a hematologic toxicity (cytopenia Grade 3 or 4) lasts for more than 42 days without recovery to at least a Grade 2, despite TKI interruption and adequate management (including hematopoietic growth factors), then the patient must be discontinued from the study treatment.		
Neutropenia (ANC)		

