> 3.0 - 5.0 x ULN	Recommendation: Maintain dose level. Repeat LFTs ^b as soon as possible, preferably within 48-72 hours from awareness of the abnormal results; if abnormal lab values are confirmed upon the repeat test, then monitor LFTs ^b weekly, or more frequently if clinically indicated, until resolved to ≤ 3.0 x ULN	Recommendation: Maintain dose level. Repeat LFTs ^b as soon as possible, preferably within 48-72 hours from awareness of the abnormal results; if abnormal lab values are confirmed upon the repeat test, then monitor LFTs ^b weekly, or more frequently if clinically indicated, until resolved to ≤ 3.0 x ULN

[figure not shown]
Dose modifications for both asciminib and bosutinib Please note that if a patient requires a dose interruption of > 28 days for each toxicity, then the patient must be discontinued from the study treatment		
Worst toxicity CTCAE Grade 4.03	Asciminib	Bosutinib
> 5.0 - 10.0 x ULN	Mandatory: Hold dose. Repeat LFTs ^b as soon as possible, preferably within 48-72 hours from awareness of the abnormal results; monitor LFTs ^b weekly, or more frequently if clinically indicated, until resolved to ≤ 3.0 x ULN: Then If resolved in ≤ 14 days, maintain dose level If resolved in > 14 days, reduce dose ↓ 1 dose level	Mandatory: Hold dose. Repeat LFTs ^b as soon as possible, preferably within 48-72 hours from awareness of the abnormal results; monitor LFTs ^b weekly, or more frequently if clinically indicated, until resolved to ≤ 2.5 x ULN: Then Recommendation: If resolved in ≤ 28 days, reduce dose ↓ 1 dose level Recommendation: If resolved in > 28 days, Discontinue patient from study drug treatment
> 10.0 - 20.0 x ULN	Mandatory: Hold dose. Repeat LFTs ^b as soon as possible, preferably within 48-72 hours from awareness of the abnormal results; monitor LFTs ^b weekly, or more frequently if clinically indicated, until resolved to ≤ baseline. Then reduce dose ↓ 1 dose level.	Mandatory: Hold dose. Repeat LFTs ^b as soon as possible, preferably within 48-72 hours from awareness of the abnormal results; monitor LFTs ^b weekly, or more frequently if clinically indicated, until resolved to ≤ 2.5 x ULN. Then Recommendation: If resolved in ≤ 28 days, reduce dose ↓ 1 dose level maintain dose level Recommendation: If resolved in > 28 days, Discontinue patient from study drug treatment.

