> 20.0 x ULN	Mandatory: Hold dose. Repeat LFTs ^b as soon as possible, preferably within 48-72 hours from awareness of the abnormal results; monitor LFTs ^b weekly, or more frequently if clinically indicated, until resolved to ≤ 3 x ULN (or ≤ 5 x ULN for patients with baseline value > 3.0 -5.0 x ULN), then resume treatment at reduce dose ↓ 1 dose level. Only 1 dose reduction is allowed; if reoccurs at > 5 x ULN, discontinue patient from study drug treatment.	Mandatory: Hold dose. Repeat LFTs ^b as soon as possible, preferably within 48-72 hours from awareness of the abnormal results; monitor LFTs ^b weekly, or more frequently if clinically indicated, until resolved to ≤ 2.5 x ULN (then Recommendation: If resolved in ≤ 28 days, reduce dose ↓ 1 dose level maintain dose level Recommendation: If resolved in > 28 days, Discontinue patient from study drug treatment

Dose modifications for both asciminib and bosutinib		
Please note that if a patient requires a dose interruption of > 28 days for each toxicity, then the patient must be discontinued from the study treatment		
Worst toxicity CTCAE Grade 4.03	Asciminib	Bosutinib
Combined ^c elevations of AST or ALT and total bilirubin		
For patients with normal baseline ALT and AST and total bilirubin value: AST or ALT >3.0 x ULN combined with total bilirubin >2.0 x ULN without evidence of cholestasis ^d For patients with elevated baseline AST or ALT or total bilirubin value [AST or ALT >2 x baseline AND > 3.0 x ULN]	Mandatory: Permanently discontinue patient from study drug treatment. Repeat as soon as possible, preferably within 48 hours from awareness of the abnormal results, then with weekly monitoring of LFTs ^b), or more frequently if clinically indicated, until AST, ALT, or bilirubin have resolved to baseline or stabilization over 4 weeks. Refer to Section 6.3.3.1 for additional follow-up evaluations as applicable.	Mandatory: Permanently discontinue patient from study drug treatment. Repeat as soon as possible, preferably within 48 hours from awareness of the abnormal results, then with weekly monitoring of LFTs ^b), or more frequently if clinically indicated, until AST, ALT, or bilirubin have resolved to baseline or stabilization over 4 weeks. Refer to Section 6.3.3.1 for additional follow-up evaluations as applicable.
Investigation (metabolic)		
Asymptomatic amylase and/or lipase elevation		

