Grade 1	Recommendation: Maintain dose level. Consider to initiate appropriate skin toxicity therapy (such as antihistamines, topical corticosteroids and low-dose systemic corticosteroids)	Recommendation: Maintain dose level. Consider to initiate appropriate skin toxicity therapy (such as antihistamines, topical corticosteroids and low-dose systemic corticosteroids)
Grade 2	Recommendation: Maintain dose level, but initiate/intensify appropriate skin toxicity therapy (such as antihistamines, topical corticosteroids and low-dose systemic corticosteroids)	Recommendation: Maintain dose level, but initiate/intensify appropriate skin toxicity therapy (such as antihistamines, topical corticosteroids and low-dose systemic corticosteroids)
Grade 3, despite skin toxicity therapy	Recommendation: Hold dose until resolved to Grade ≤ 1, then: If resolved in ≤ 7 days, then reduce dose ↓ 1 dose level If resolved in > 7 days (despite appropriate skin toxicity therapy), then discontinue patient from study drug treatment	Recommendation: Hold dose until resolved to Grade ≤ 1, then: If resolved in ≤ 7 days, then reduce dose ↓ 1 dose level If resolved in > 7 days (despite appropriate skin toxicity therapy), then discontinue patient from study drug treatment
Grade 4, despite skin toxicity therapy	Mandatory: Permanently discontinue patient from study drug treatment.	Mandatory: Permanently discontinue patient from study drug treatment.
General disorders and administration site conditions		
Fatigue/ Asthenia		
Grade 1 or 2	Recommendation: Maintain dose level	Recommendation: Maintain dose level
Grade 3	Recommendation: Hold dose until resolved to ≤ grade 1, then : If resolved in ≤ 7 days, then maintain dose level If resolved in > 7 days, then reduce dose ↓ 1 dose level	Recommendation: Hold dose until resolved to ≤ grade 1, then : If resolved in ≤ 7 days, then maintain dose level If resolved in > 7 days, then reduce dose ↓ 1 dose level
All dose modifications should be based on the worst preceding toxicity.		
^a Common Toxicity Criteria for Adverse Events (CTCAE Version 4.03)		
^b Core LFTs consist of ALT, AST, total bilirubin (fractionated [direct and indirect], if total bilirubin > 2.0 x ULN), and alkaline phosphatase (fractionated [quantification of isoforms], if alkaline phosphatase > 2.0 x ULN.)		
^c “Combined” defined as total bilirubin increase to the defined threshold concurrently with ALT/AST increase to the defined threshold		

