Dose modifications for both asciminib and bosutinib		
Please note that if a patient requires a dose interruption of > 28 days for each toxicity, then the patient must be discontinued from the study treatment		
Worst toxicity CTCAE Grade 4.03	Asciminib	Bosutinib

If combined elevations of AST or ALT and total bilirubin do not meet the defined thresholds, please follow the instructions for isolated elevation of total bilirubin and isolated elevation of AST/ALT, and take a conservative action based on the degree of the elevations (e.g. discontinue treatment at the situation when hold dose is needed for one parameter and discontinue treatment is required for another parameter). After all elevations resolve to the defined thresholds that allow treatment re-initiation, re-start the treatment either at the same dose or at one dose lower if meeting a criterion for dose reduction
 
^d “Cholestasis” defined as ALP elevation (>2.0 x ULN and R value <2) in patients without bone metastasis, or elevation of ALP liver fraction in patients with bone metastasis
 
Note: The R value is calculated by dividing the ALT by the ALP, using multiples of the ULN for both values. It denotes whether the relative pattern of ALT and/or ALP elevation is due to cholestatic (R ≤ 2), hepatocellular (R ≥ 5), or mixed (R >2 and < 5) liver injury
 
* Note: If total bilirubin > 3.0 x ULN is due to the indirect (non-conjugated) component only, and hemolysis as the etiology has been ruled out as per institutional guidelines (e.g., review of peripheral blood smear and haptoglobin determination), then ↓ 1 dose level and continue treatment at the discretion of the investigator.
 
** Note: A CT scan or other imaging study to assess the pancreas, liver, and gallbladder must be performed within 1 week of the first occurrence of any ≥ Grade 3 of amylase and/or lipase. If asymptomatic Grade 2 elevations of lipase and/or amylase occur again at the reduced dose, patients will be discontinued permanently from study treatment.
 
*** Note: antidiarrheal medication is recommended at the first sign of abdominal cramping, loose stools or overt diarrhea
		

[figure not shown]

Table 6-3 Dose reduction steps for asciminib and bosutinib

Dose reduction*			
	Starting dose level – 0	Dose level – 1	
Asciminib BID	40 mg tablet BID (total daily dose 80 mg)	20 mg tablet BID (total daily dose 40 mg)	
*Dose reduction should be based on the worst toxicity demonstrated at the last dose.			

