7.2.2.5 Laboratory evaluations

Central laboratory will be used for analysis of hematology, biochemistry, coagulation, serum pregnancy and hepatitis marker specimens collected (safety monitoring) as specified in Table 7-1, Table 7-2 and Table 7-5. Details on the collections, shipment of the samples and reporting of results by the central laboratory are provided to investigators in the [CABL001A2301 Laboratory Manual]. The time windows granted for laboratory evaluations are identical with the corresponding visit time windows for each visit (see Section 7.1.5).

Local laboratory analysis are allowed if there is a clinical suspicion of abnormal laboratory values which is supported by a reported adverse event and for hematology assessments at Week 6, 10 and 14.

[figure not shown]
[figure not shown]

Table 7-5 Central clinical laboratory parameters collection plan

Test Category	Test Name	Frequency
Hematology	Hemoglobin, platelets, red blood cells, white blood cells, WBC morphology with differential (basophils, eosinophils, lymphocytes, monocytes, neutrophils, promyelocytes, myelocytes, metamyelocytes, blast and other)	Screening/baseline, Week 1 Day 1, Week 2 Day 1, every 2 weeks from week 4 up to week 16, every 4 weeks up to week 96, and every 12 weeks thereafter, EOT and as clinically indicated / S-Screening/S-baseline*, S-Week 1 Day 1, S-Week 2 Day 1, every 2 weeks from S-week 4 up to S-week 16, every 4 weeks up to S-week 96, and every 12 weeks thereafter, S-EOT and as clinically indicated
Chemistry	Hemoglobin A1c	Screening/baseline, Week 12 and as clinically indicated / S-Screening/S-baseline*, S-Week 12 and as clinically indicated
Chemistry	Creatinine clearance	Screening/baseline / S-Screening/S-baseline*
Chemistry	Albumin, alkaline phosphatase, ALT (SGPT), AST (SGOT), total calcium, total calcium (corrected for albumin), creatinine, creatine kinase, potassium, magnesium, sodium, phosphate (inorganic phosphorus), direct bilirubin, indirect bilirubin, total bilirubin, total cholesterol, LDL cholesterol, HDL cholesterol, total protein, triglycerides, blood urea or Blood Urea Nitrogen (BUN), uric acid, amylase, lipase, glucose (fasting)	Screening/baseline, Week 1 Day 1, Week 2 Day 1, every 4 weeks from week 4 up to week 96, and every 12 weeks thereafter, EOT, and as clinically indicated / S-Screening/S-baseline*, S-Week 1 Day 1, S-Week 2 Day 1, every 4 weeks from S-week 4 up to S-week 96, and every 12 weeks thereafter, S-EOT, and as clinically indicated

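### Table 6-2 lets asciminib restart at a higher enzyme level after an AST/ALT rise above 20 x ULN than after a rise of 10 to 20 x ULN

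*Combined protocol and SAP*

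**What the plan says.** Table 6-2 has three mandatory holds for isolated AST/ALT elevation in the asciminib column:

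- **> 5–10 x ULN:** hold until ≤ 3.0 x ULN; same dose if that takes 14 days or less, otherwise one level down.
- **> 10–20 x ULN:** hold "until resolved to ≤ baseline", then one level down.
- **> 20 x ULN:** hold until ≤ 3 x ULN, or ≤ 5 x ULN "for patients with baseline value > 3.0 -5.0 x ULN", then one level down. This row adds: "Only 1 dose reduction is allowed; if reoccurs at > 5 x ULN, discontinue patient from study drug treatment".

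A table footnote settles which row applies: "All dose modifications should be based on the worst preceding toxicity". Section 6.3.1 allows no departure from mandatory interruptions or reductions. It also ends treatment "If a patient requires a dose interruption of > 28 days for each non-hematologic toxicity". One level down is 20 mg twice daily (Table 6-3). Inclusion criterion 7 (Section 5.2) limits AST and ALT at entry to 3.0 x ULN. The bosutinib column uses ≤ 2.5 x ULN in all three rows.

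**The concern.** A restart ceiling should not rise as the event gets worse. Here it falls from the first row to the second and then returns to 3 x ULN in the third. Because the worst preceding toxicity governs, a patient who peaks above 20 x ULN cannot be managed under the stricter middle row. A site that follows the table may therefore re-expose a patient after the most severe isolated transaminase rise at an enzyme level the table forbids after a milder one. The 28-day limit can widen the contrast: the milder case may time out waiting for baseline while the worse case is already eligible to restart. I found no footnote or other text that reconciles the rows, and no other asciminib entry in Table 6-2 whose restart condition loosens as severity grows.

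**Working it through.** No figure in the plan needs reproducing; the check is on the order of the thresholds. Let b be baseline in multiples of ULN. The asciminib ceilings are 3.0 after > 5–10, b after > 10–20, and after > 20 either 3.0 (b ≤ 3.0) or 5.0 (3.0 < b ≤ 5.0).

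| b | > 5–10 | > 10–20 | > 20 | > 20 minus > 10–20 |
|---|---|---|---|---|
| 0.5 | 3.0 | 0.5 | 3.0 | 2.5 |
| 1.0 | 3.0 | 1.0 | 3.0 | 2.0 |
| 2.0 | 3.0 | 2.0 | 3.0 | 1.0 |
| 3.0 | 3.0 | 3.0 | 3.0 | 0 |
| 4.0 | 3.0 | 4.0 | 5.0 | 1.0 |

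For every b below 3.0 the worst row is looser by 3.0 − b. Criterion 7 puts essentially every randomised patient there or exactly at 3.0, where the rows agree. A baseline above 3.0 could arise only for a patient switching from bosutinib, because the switch conditions in Section 7.1.2.2 set no AST/ALT limit beyond resolution of Grade 3–4 toxicity.

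**Effect of the 28-day limit (illustration).** Assume a log-linear fall with a halving time h of 3, 5 or 7 days; the documents give no decay rate. Days on hold = h × log2(peak/ceiling). With b = 0.5:

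- Peak 15 x ULN, ceiling 0.5: log2(30) = 4.91, so 14.7, 24.5 or 34.3 days.
- Peak 25 x ULN, ceiling 3.0: log2(8.33) = 3.06, so 9.2, 15.3 or 21.4 days.

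At h = 7 the milder event forces discontinuation and the worse one may resume.

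**Cost of a shared ceiling of max(b, 1.0).** The extra hold after > 20 x ULN is h × log2(3/max(b, 1.0)), whatever the peak:

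- b ≤ 1.0: 1.585 halving times, so 7.9 days (4.8–11.1 for h of 3–7).
- b = 2.0: 0.585 halving times, so 2.9 days (1.8–4.1).

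From an assumed 25 x ULN peak with b ≤ 1.0, the total hold is 4.64h: 13.9, 23.2 or 32.5 days. The 28-day limit is passed if h exceeds 28/4.64 = 6.0 days, against 28/3.06 = 9.2 days under the present 3 x ULN ceiling. For an assumed 40 x ULN peak the thresholds are 28/5.32 = 5.3 and 28/3.74 = 7.5 days. Liver tests during a hold may be only weekly, so these totals are approximate.

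**Why a ULN floor.** With a bare baseline ceiling, b = 0.5, a 25 x ULN peak and h = 5, the hold is 5 × log2(50) = 28.2 days. That patient could be discontinued with enzymes already in the normal range.

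**The case against.** The strongest reply is that only one element of the rule is out of order. The dose consequences do escalate: maintain or reduce, then reduce, then reduce once only with a stop on recurrence above 5 x ULN. Section 6.3.1 also requires discontinuation if toxicity returns at the same or worse severity after a reduced-dose restart. Restart is at half dose, the 3 x ULN ceiling equals the entry limit, and Section 7.1.6 tells the investigator to stop if continuing would be detrimental. All of this stands and keeps the effect modest. It does not reconcile the ceilings, and both recurrence stops act only after re-exposure.

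Two stronger readings are tempting. A reader might infer that the baseline in this table is undefined, since chemistry is scheduled at "Screening/baseline, Week 1 Day 1, Week 2 Day 1, every 4 weeks from week 4 up to week 96". But that list treats Screening/baseline and Week 1 Day 1 as separate visits, as do Section 7.1.2 and Table 7-1, and Table 7-6 adds S-Baseline for switch patients. A cross-reference is enough.

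A reader might also infer that the > 20 x ULN cell is the mistake. The text does not settle this. The neighbouring asciminib rows both use 3 x ULN, which makes the baseline ceiling look like the outlier; elsewhere the asciminib column is never looser for worse events, which points to the > 20 cell.

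**Conclusion.** Wrong as written: a mandatory safety rule whose restart ceiling is looser after > 20 x ULN than after > 10–20 x ULN for any baseline below 3 x ULN. The gap is 3.0 minus baseline, or 2.0 x ULN at a baseline of 1.0. This rests only on the table entries and the entry limit. The gap compares ceilings, not risks. The documents give no frequency of AST/ALT above 10 x ULN, so the number of patients affected is unknown. A reader might look for bias in the Week 24 comparison. Nothing in the documents supports that, and no sample size, power or alpha figure depends on this rule. It should be corrected for consistent patient protection.

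**What to change.** Give the > 10–20 and > 20 x ULN asciminib rows one ceiling, for example: *hold until the value is no higher than baseline or ULN, whichever is greater, then resume one dose level lower.* Delete the ≤ 5 x ULN alternative. Keep the single-reduction limit and the stop on recurrence above 5 x ULN in the > 20 row. Add a note that baseline means the Screening/Baseline visit, or S-Baseline for switch patients.

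For a baseline below ULN this relaxes the > 10–20 row: at 0.5 x ULN it shortens the hold by log2(1.0/0.5) = 1 halving time. For a switch patient with a baseline above 3.0 x ULN the shared ceiling would still exceed that of the > 5–10 row, so the sponsor may wish to cap it at 3 x ULN.

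The change needs a written amendment with the approvals in Section 12.1. Recruitment closed on 22 October 2019 with 233 randomised (Amendment 03-US.01 rationale), so it can help only patients still on asciminib or switching to it. A few patients with a > 20 x ULN event would be held longer, as computed above, and some could reach the 28-day limit. Discontinuation is a treatment-failure event (Section 10.5.2) and counts as non-response at later visits (Sections 10.4.3 and 10.5.1). Each patient so lost who would otherwise have been in MMR at a given visit lowers that visit's asciminib rate by 1/148 = 0.68 percentage points, using the planned arm size.

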6.3.3.1 Follow up on potential drug-induced liver injury (DILI) cases

Patients with transaminase increase combined with TBIL increase may be indicative of potential DILI, and should be considered as clinically important events.

The threshold for potential DILI may depend on the patient's baseline AST/ALT and TBIL value; patients meeting any of the following criteria will require further follow-up as outlined below:

- For patients with normal ALT and AST and TBIL value at baseline: AST or ALT > 3.0 x ULN combined with TBIL > 2.0 x ULN
- For patients with elevated AST or ALT or TBIL value at baseline: [AST or ALT > 2 x baseline AND > 3.0 x ULN] OR [AST or ALT > 8.0 x ULN], combined with [TBIL > 2 x baseline AND > 2.0 x ULN]

Medical review needs to ensure that liver test elevations are not caused by cholestasis, defined as ALP elevation > 2.0 x ULN with R value < 2 in patients without bone metastasis, or elevation of ALP liver fraction in patients with bone metastasis.

Note: (The R value is calculated by dividing the ALT by the ALP, using multiples of the ULN for both values. It denotes whether the relative pattern of ALT and/or ALP elevation is due to cholestatic ($R \leq 2$), hepatocellular ($R \geq 5$), or mixed ($R > 2$ and < 5) liver injury).

In the absence of cholestasis, these patients should be immediately discontinued from study drug treatment, and repeat LFT testing as soon as possible, preferably within 48 hours from the awareness of the abnormal results. The evaluation should include laboratory tests, detailed history, physical assessment and the possibility of liver metastasis or new liver lesions, obstructions/compressions, etc.

1. Laboratory tests should include ALT, AST, albumin, creatinine kinase, total bilirubin, direct and indirect bilirubin, GGT, prothrombin time (PT)/INR and alkaline phosphatase.
2. A detailed history, including relevant information, such as review of ethanol, concomitant medications, herbal remedies, supplement consumption, history of any pre-existing liver conditions or risk factors, should be collected.
3. Further testing for acute hepatitis A, B, C or E infection and liver imaging (e.g. biliary tract) may be warranted.

4. Obtain PK sample, as close as possible to last dose of study drug, if PK analysis is performed in the study.

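### Table 6-2, combined AST/ALT and bilirubin row: the raised-baseline line lacks the bilirubin threshold and cholestasis exception that Section 6.3.3.1 gives for the same patients

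*Combined protocol and SAP*

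**What the plan says.** Section 6.3.1 gives Table 6-2 binding force: "Permanent treatment discontinuation is mandatory for specific events indicated as such in" that table. The row on combined elevations of AST or ALT and total bilirubin carries such an instruction, in the same words for asciminib and bosutinib. It has two trigger lines.

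- **Normal baseline:** "AST or ALT >3.0 x ULN combined with total bilirubin >2.0 x ULN without evidence of cholestasis".
- **Raised baseline:** "For patients with elevated baseline AST or ALT or total bilirubin value [AST or ALT >2 x baseline AND > 3.0 x ULN", where the bracket closes and the line ends.

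Footnote c explains that a combined elevation is "defined as total bilirubin increase to the defined threshold concurrently with ALT/AST increase to the defined threshold". Where combined elevations "do not meet the defined thresholds, please follow the instructions for isolated elevation of total bilirubin and isolated elevation of AST/ALT", sites use those two isolated rows instead. Footnote d describes cholestasis as "defined as ALP elevation (>2.0 x ULN and R value <2) in patients without bone metastasis"; its marker is on the normal-baseline line only. The action cell points to the liver-injury section for one purpose: "Refer to Section 6.3.3.1 for additional follow-up evaluations as applicable".

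Section 6.3.3.1 opens its raised-baseline criterion with the same AST/ALT bracket. It then adds an alternative of AST or ALT above 8.0 x ULN and requires either to be "combined with [TBIL > 2 x baseline AND > 2.0 x ULN". Next, for both baseline groups, it asks for a medical review to rule out cholestasis, and it calls for immediate discontinuation only when cholestasis is absent.

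**The concern.** The protocol states the trigger for a mandatory, permanent action twice, and the two statements differ for patients who enter with a raised liver test. The table line appears to carry only the first clause of the Section 6.3.3.1 rule. Footnote c relies on a bilirubin threshold that the table never gives for this group. The same missing threshold is what should separate this row from the milder isolated rows. The cholestasis exception is attached only to patients with a normal baseline.

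A site working from the table alone could permanently stop a patient whom the protocol's own liver-injury rule does not require to be stopped. Under Section 10.4.3, stopping before week 24 also makes the patient a non-responder for the primary endpoint.

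**Working it through.** The plan has no figure to reproduce here. The check compares the two texts element by element and then applies both to one patient.

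**Raised-baseline rule in each place**

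| Element | Table 6-2, combined row | Section 6.3.3.1 |
|---|---|---|
| AST/ALT | > 2 x baseline and > 3.0 x ULN | the same, or > 8.0 x ULN |
| Bilirubin | no figure; footnote c presumes one | > 2 x baseline and > 2.0 x ULN |
| Cholestasis | no exception on this line | stop ordered only if absent |
| Action | permanent stop, mandatory | immediate stop |

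The missing > 8.0 x ULN alternative makes no difference in this trial. Inclusion criterion 7 caps baseline AST and ALT at 3.0 x ULN, so twice baseline is at most 2 x 3.0 = 6.0 x ULN. Any value above 8.0 already meets the first bracket. Only the bilirubin and cholestasis omissions matter.

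**Illustrative patient** (values assumed, in multiples of ULN; the baseline is permitted by criterion 7)

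- Baseline: ALT 1.4, bilirubin 0.8. ALT is above normal, so the raised-baseline line applies.
- On treatment: ALT 3.2, bilirubin 2.4, ALP 2.5; no bone metastasis.

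1. AST/ALT condition: 2 x 1.4 = 2.8. 3.2 > 2.8 and 3.2 > 3.0, so it is met in both texts.
2. Bilirubin condition in Section 6.3.3.1: 2 x 0.8 = 1.6. 2.4 > 1.6 and 2.4 > 2.0, so it is met. A bilirubin of 2.4 also exceeds the normal-baseline line's 2.0, so the result does not depend on which threshold a site takes the table to mean.
3. Cholestasis: ALP 2.5 > 2.0, and R = ALT/ALP = 3.2/2.5 = 1.28 < 2. Both parts of the definition are met.
4. Result: the table's raised-baseline line requires permanent discontinuation. Section 6.3.3.1 does not order it, because cholestasis is present.

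A patient with the same on-treatment values but normal baseline tests would be exempt under the table's own first line (3.2 > 3.0 and 2.4 > 2.0, but cholestasis present). Within the table, then, the exception depends only on the baseline value.

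If the same ALT 1.4 to 4.0 and bilirubin 0.8 to 2.5 rise occurs **without** cholestasis, the texts agree: 4.0 > 2.8 and > 3.0, and 2.5 > 1.6 and > 2.0, so both stop the patient.

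**The case against.** **The cell may have been cut off in extraction.** Its text equals the first clause of the Section 6.3.3.1 rule, square brackets included, and such brackets serve little purpose around a stand-alone condition. Other parts of Table 6-2 also look incomplete. Against this, the bracket closes, the neighbouring action cells are complete, and no page header falls between this row and the next. Only one copy of the table is available here, so the doubt stands and lowers confidence.

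**Section 6.3.3.1 already holds the full rule.** True, and the row names that section. But it does so for follow-up evaluations, not for the trigger, and nothing says which text governs. This limits the importance of the point without removing it.

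**A reader might infer that the line stops patients for an ALT rise alone.** The documents do not support this. The row heading and footnote c both require a concurrent bilirubin rise, and isolated AST/ALT rises have their own rows.

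**A reader might also infer that sites will apply the 2.0 x ULN bilirubin limit from the line above, and so stop patients with raised baseline bilirubin too early.** Nothing tells them to. That line is confined to normal baselines, and Section 6.3.3.1 says the threshold may depend on baseline. Nor would such a patient simply continue otherwise. For bilirubin above 1.5 to 3.0 x ULN, the isolated row recommends a hold until 1.5 x ULN or lower, and Section 6.3.1 requires discontinuation if an interruption for a non-hematologic toxicity exceeds 28 days. What stands is only that the table leaves the threshold undefined.

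**The error is on the cautious side.** This is fair. Footnote c itself asks for a conservative action when elevations fall short of the combined thresholds.

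**Conclusion.** The point holds as a minor inconsistency between table and text, with low to medium confidence, provided the source PDF reads as the extracted text does. The firm part is cholestasis: for a raised-baseline patient who meets every AST/ALT and bilirubin threshold but is cholestatic, the table requires a permanent stop that Section 6.3.3.1 does not order. The second part is that the table gives no bilirubin trigger for raised-baseline patients, so footnote c cannot be applied to them from the table alone.

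This does not mean that Section 6.3.3.1 tells sites to keep treating a cholestatic patient. It only withholds the immediate stop. In the worked example the isolated rows would recommend maintaining the dose for the ALT value and holding it for the bilirubin value.

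The number affected is unknown and probably small. It takes a raised baseline, AST/ALT above 3.0 x ULN on treatment and a concurrent bilirubin rise, and exclusion criterion 9 (liver disease history) narrows the group. The wording is the same in both arms, and power and alpha are unaffected. A wrong stop before week 24 would count as non-response, but the documents do not allow that effect to be sized.

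**What to change.** Check the source PDF for a lost line first. If the text is there, no change is needed. If it is absent, restate the raised-baseline line of the combined row so that it requires all of the following:

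- AST or ALT above 2 x baseline and above 3.0 x ULN, or AST or ALT above 8.0 x ULN;
- total bilirubin above 2 x baseline and above 2.0 x ULN;
- no evidence of cholestasis, with the footnote d marker added to this line.

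Send sites a short clarification that this is the trigger for the permanent stop. A listing of patients already stopped under this row is optional.

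The cost is one table cell filled from existing protocol text and one notice, with no new procedures, data or patients. Recruitment closed on 22-Oct-2019, so the correction can help only patients still on treatment.
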